### **9.5.3 Biomarkers**

See [Section 9.5.1](#).

## 9.7 Interim analyses

No interim analysis is planned.

## 9.8 Sample size calculation

In CHOIR (Mitchell 2002), treatment with Omapatrilat was associated with an approximately ~10% reduction in characteristic impedance at 12 weeks, with little or no change seen amongst enalapril- treated patients. Based on a similar study design and population, and accounting for a dropout rate of 20% from first visit to subsequent follow up and a 10% rate of non-evaluable data, assuming a standard deviation of 80 for the primary efficacy variable and 90% power, a sample size of 432 subjects (216 per arm) will be necessary to detect a clinically important change of 30 dyne x sec/cm^5 between the two treatment groups.

Assuming a significance level of 0.05, a sample size 432 patients would provide 88% power to detect a 25% reduction in the geometric mean of the proportional change from baseline to Week 12 in NT-proBNP for the sacubitril/valsartan treatment group assuming a value of 0.95 for the enalapril group, a value of 0.7125 for the sacubitril/valsartan group (25% reduction), a common standard deviation of 0.85 and a 20% drop-out rate. The difference between the logs for the two treatment groups is therefore assumed to be 0.288.

## 10 Ethical considerations

### 10.1 Regulatory and ethical compliance

This clinical study was designed and shall be implemented, executed and reported in accordance with the ICH Harmonized Tripartite Guidelines for Good Clinical Practice, with applicable local regulations (including European Directive 2001/20/EC, US CFR 21, and Japanese Ministry of Health, Labor, and Welfare), and with the ethical principles laid down in the Declaration of Helsinki.

### 10.2 Informed consent procedures

Eligible patients/subjects may only be included in the study after providing written (witnessed, where required by law or regulation), IRB/IEC-approved informed consent, or, if incapable of doing so, after such consent has been provided by a legally acceptable representative(s) of the patient. In cases where the patient's representative gives consent, the patient must be informed about the study to the extent possible given his/her understanding. If the patient is capable of doing so, he/she must indicate assent by personally signing and dating the written informed consent document or a separate assent form. Informed consent must be obtained before conducting any study-specific procedures (e.g., all of the procedures described in the protocol). The process of obtaining informed consent must be documented in the patient source documents.

Novartis will provide to investigators in a separate document a proposed informed consent form that complies with the ICH GCP guideline and regulatory requirements and is considered appropriate for this study. Any changes to the proposed consent form suggested by the investigator must be agreed to by Novartis before submission to the IRB/IEC, and a copy of the approved version must be provided to the Novartis monitor after IRB/IEC approval. Women of

child-bearing potential must be informed that taking the study treatment may involve unknown risks to the fetus if pregnancy were to occur during the study and agree that in order to participate in the study they must adhere to the contraception requirement for the duration of the study. If there is any question that the patient will not reliably comply, they must not be entered in the study.

### **10.3 Responsibilities of the investigator and IRB/IEC**

Before initiating a trial, the investigator/institution must obtain approval/favorable opinion from the Institutional Review Board/Independent Ethics Committee (IRB/IEC) for the trial protocol, written informed consent form, consent form updates, subject recruitment procedures (e.g., advertisements) and any other written information to be provided to patients/subjects. Prior to study start, the investigator is required to sign a protocol signature page confirming his/her agreement to conduct the study in accordance with these documents and all of the instructions and procedures found in this protocol and to give access to all relevant data and records to Novartis monitors, auditors, Novartis Quality Assurance representatives, designated agents of Novartis, IRBs/IECs, and regulatory authorities as required. If an inspection of the clinical site is requested by a regulatory authority, the investigator must inform Novartis immediately that this request has been made.

### **10.4 Publication of study protocol and results**

The key design elements of this protocol will be posted in a publicly accessible database such as [clinicaltrials.gov](http://clinicaltrials.gov). In addition, upon study completion and finalization of the study report the results of this trial will be either submitted for publication and/or posted in a publicly accessible database of clinical trial results.

### **10.5 Quality Control and Quality Assurance**

Novartis maintains a robust Quality Management (QM) system that includes all activities involved in quality assurance and quality control, including the assignment of roles and responsibilities, the reporting of results, and the documentation of actions and escalation of issues identified during the review of quality metrics, incidents, audits and inspections.

Audits of investigator sites, vendors, and Novartis systems are performed by Novartis Pharma Auditing and Compliance Quality Assurance (CQA), a group independent from those involved in conducting, monitoring or performing quality control of the clinical trial. The clinical audit process uses a knowledge/risk based approach.

Audits are conducted to assess GCP compliance with global and local regulatory requirements, protocols and internal SOPs, and are performed according to written Novartis processes.

## **11 Protocol adherence**

This protocol defines the study objectives, the study procedures and the data to be collected on study participants. Additional assessments required to ensure safety of patients/subjects should be administered as deemed necessary on a case-by-case basis. Under no circumstances is an

investigator allowed to collect additional data or conduct any additional procedures for any research related purpose involving any investigational drugs under the protocol.

Investigators ascertain they will apply due diligence to avoid protocol deviations. If an investigator feels a protocol deviation would improve the conduct of the study this must be considered a protocol amendment, and unless such an amendment is agreed upon by Novartis and approved by the IRB/IEC and health authorities, where required, it cannot be implemented.

## **11.1 Protocol amendments**

Any change or addition to the protocol can only be made in a written protocol amendment that must be approved by Novartis, health authorities where required, and the IRB/IEC prior to implementation. Only amendments that are intended to eliminate an apparent immediate hazard to patients/subjects may be implemented immediately provided the health authorities are subsequently notified by protocol amendment and the reviewing IRB/IEC is notified. Notwithstanding the need for approval of formal protocol amendments, the investigator is expected to take any immediate action required for the safety of any patient included in this study, even if this action represents a deviation from the protocol. In such cases, the reporting requirements identified in [Section 7](#) Safety Monitoring must be followed.

## **13 Appendix 1: Clinically notable laboratory values and vital signs**

Clinically notable vital signs will be defined in this study as a SBP < 90 mmHg. The study treatment shall be interrupted or stopped based on investigator judgement.

Clinically notable laboratory abnormalities for selected tests based on a percent change from baseline:

### **Hematology**

RBC count	>50% increase, >20% decrease
Hemoglobin	>50% increase, >20% decrease
Hematocrit	>50% increase, >20% decrease
WBC count	>50% increase, >50% decrease
Platelet count	>75% increase, >50% decrease

### **Blood Chemistry**

ALT (SGPT)	>150% increase
AST (SGOT)	>150% increase
BUN	>50% increase
Creatinine	>50% increase
Total bilirubin	>100% increase
CPK	>300% increase
Alkaline phosphatase	>100% increase
Potassium	>20% increase, >20% decrease
Chloride	>10% increase, >10% decrease
Calcium	>10% increase, >10% decrease
Uric acid	>50% increase

## 14 Appendix 2: Treatment guidelines for hyperkalemia (serum potassium greater than or equal to 5.5 mEq/L)

### General principles

Elevation of potassium levels above the predefined values should be repeated and confirmed before any action is taken.

Any patient who experiences a potassium level  $\geq 5.5$  mEq/L confirmed by repeated testing after randomization requires regular, repeated checks of potassium concentration (beyond that prescribed in the protocol) until it is clear that the potassium concentration is stable and not rising into the range of concern ( $\geq 5.5$  mEq/L).

Patients with elevated potassium value will be managed according to the corrective actions outlined below and the investigator's clinical judgement. Hyperkalemia should be followed until resolution.

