### **5.6.2 Discontinuation of study treatment**

Discontinuation of study treatment for a patient occurs when study drug is stopped earlier than the protocol planned duration, and can be initiated by either the patient or the investigator.

The investigator must discontinue study treatment for a given patient if, on balance, he/she believes that continuation would negatively impact the risk/benefit of trial participation.

Patients may voluntarily discontinue the study drug for any reason at any time.

Study treatment must be discontinued under the following circumstances:

- Patient wish
- Withdrawal of consent
- Pregnancy (see [Section 6.5.8](#) and [Section 7.6](#))
- Use of prohibited treatment as per recommendations in [Table 5-9](#)
- Any protocol deviation that constitutes a risk to the patient

- Any situation in which study participation might result in a safety risk to the patient
- Unresolved worsening HF

Study medication may be discontinued at the investigator's discretion if any of the following serious suspected drug-related AEs occur:

- Symptomatic hypotension
- Suspected occurrence of angioedema. A patient with any signs or symptoms of clinically significant angioedema should be thoroughly evaluated by the investigator to determine if it constitutes a reason for discontinuation of study medication.
- Any laboratory abnormalities that in the judgment of the investigator, taking into consideration the subject's overall status, prevents the subject from continuing participation in the study.

Depending on the serum potassium, blood pressure, or eGFR, patients may need to have their study drug dose or the dose of another concomitant medication reduced or discontinued; or, if appropriate, have potentially contributing agents adjusted. Refer to appendices for treatment guidelines for hyperkalemia, hypotension or renal dysfunction, respectively.

If discontinuation of study treatment occurs, the patient should NOT be considered withdrawn from the study. The investigator must determine the primary reason for the patient's premature discontinuation of study treatment and record this information on End of Study Treatment eCRF. After study treatment discontinuation, the patient should attend the regularly scheduled visits and have all study assessments performed.

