### Recommended corrective action for management of hyperkalemia

#### Serum potassium > 5.3 and less than or equal to 5.5 mEq/L

- Confirm potassium concentration in a non-hemolyzed sample
- Reinforce low potassium diet and restriction of food/drinks with high potassium content (e.g. orange juice, melon, bananas, low-salt substitutes etc.)
- Review medical regimen (including dietary supplements and over-the-counter medications) for agents known to cause hyperkalemia. Consider reduction in dose or discontinuation of these agents:
- Aldosterone antagonists (if they are believed to be the most likely cause of hyperkalemia)
- Potassium-sparing diuretics (e.g. amiloride and triamterene) including in combination products with thiazide or loop diuretics
- Potassium supplements, e.g., potassium chloride
- Salt substitutes
- Non-steroidal anti-inflammatory drugs (NSAIDs)
- Cyclo-oxygenase-2 (COX-2) inhibitors
- Trimethoprim and trimethoprim-containing combination products, such as Bactrim® and Septra® (trimethoprim/sulfamethoxazole fixed combination)
- Herbal Supplements:
- For example, Noni juice, alfalfa (*Medicago sativa*), dandelion (*Taraxacum officinale*), horsetail (*Equisetum arvense*), nettle (*Urtica dioica*), milkweed, lily of the valley, Siberian ginseng, hawthorn berries
- Repeat serum potassium measurement within 3 to 5 days
- If serum potassium remains  $> 5.3$  and  $\leq 5.5$  mEq/L, regularly monitor serum potassium levels to ensure stability (suggested once monthly)
- Consider down-titration of study medication, according to investigator medical judgment if he/she believes that adjustment/elimination of concomitant medications is not possible or does not alleviate the side effects of concern medical judgment.

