**Serum potassium greater than or equal to 6.0 mEq/L**

- Immediately discontinue study drug
- Confirm potassium concentration in a non-hemolyzed sample
- Urgently evaluate patient and treat hyperkalemia as clinically indicated
- Apply all measures outlined for serum potassium > 5.3 and < 6.0 mEq/L
- If serum potassium < 5.5 mEq/L, consider resumption of study drug at lower dose with repeat potassium within 5 days

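### Appendix 2 asks for a repeat potassium before any action but makes no exception at 6.0 mEq/L or more, where its own band stops study drug at once

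*Protocol*

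**What the plan says.** Section 5.6.2 of the Protocol directs sites to the appendices when potassium is a problem: "Refer to appendices for treatment guidelines for hyperkalemia, hypotension or renal dysfunction, respectively". Appendix 2 then has two layers.

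- **General principles.** "Elevation of potassium levels above the predefined values should be repeated and confirmed before any action is taken". The sentence names no level at which it ceases to apply and does not define the predefined values. The same subsection adds that patients with a raised value "will be managed according to the corrective actions outlined below", together with the investigator's clinical judgement.
- **Three bands of recommended corrective action.** These are above 5.3 up to 5.5, above 5.5 but below 6.0, and 6.0 mEq/L or more. The first two begin with confirmation in a non-hemolyzed sample. The third begins with "Immediately discontinue study drug"; only its second bullet reads "Confirm potassium concentration in a non-hemolyzed sample", and its third calls for urgent evaluation and treatment.

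**The concern.** The general sentence sets one order, confirm and then act. The top band sets the reverse, stop and then confirm. Both sit in the same appendix and both apply to the patient with the highest potassium, for whom the order matters most. A site that took the general sentence at its word could hold a stop that the band calls immediate until a repeat result came back. Because the sentence covers any action, a literal reading would also hold back the urgent evaluation and treatment listed in that band.

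Hyperkalemia is one of the major risks named in Section 3.6.1, and Section 8.4 provides no data monitoring committee, so the site instructions should not contradict each other here. What is at stake is patient safety wording. No efficacy estimate or test depends on it.

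**Working it through.** No sample-size, power or event figure is involved, so the check is a comparison of text, with one threshold comparison.

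**1. Does the general principle reach a value of 6.0?** It applies above unspecified predefined values. The documents offer two candidates:

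- 5.5 mEq/L, from the appendix title;
- 5.3 mEq/L, from the lowest band ("Serum potassium > 5.3 and less than or equal to 5.5 mEq/L") and from the dose-adjustment criterion in Table 5-7.

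6.0 − 5.5 = 0.5 mEq/L and 6.0 − 5.3 = 0.7 mEq/L. A value of 6.0 or more exceeds either candidate, so the principle applies whichever was meant.

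**2. Order of steps, side by side.**

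| Appendix 2 text | First step | Second step | Agrees with the principle? |
|---|---|---|---|
| General principles | Repeat and confirm | Act | n/a |
| Above 5.3 to 5.5 | Confirm | Diet and medication review; later, consider down-titration | Yes |
| Above 5.5 to below 6.0 | Confirm | Consider down-titration or temporary stop | Yes |
| 6.0 or more | Stop study drug immediately | Confirm | No |

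The bullets are unnumbered, so list order alone is weak evidence of a required sequence. The word *immediately* in the top band settles the point without it: a stop that waits for a repeat result is not immediate.

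**3. Is an exception written anywhere else?**

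- *Appendix 2, General principles:* refers readers to the bands and to clinical judgement, but does not say that a band overrides the confirm-first rule.
- *Table 5-7:* gives a potassium criterion for dose adjustment and says nothing on confirmation.
- *Section 5.5.6:* describes the appendices as guidance.
- *Section 5.6.2:* contains mandatory stopping rules based on risk/benefit and patient safety, none specific to potassium. It also lists laboratory abnormalities among the events for which stopping is discretionary.
- *Section 11.1:* expects immediate action for patient safety even where it is a deviation.

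None of these is an express exception for 6.0 mEq/L or more.

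**4. Size.** The conflict covers 1 of the 3 bands. An expected number of patients would need the rate of potassium at or above 6.0, and a delay would need the turnaround of the repeat sample; neither is given. The hyperkalemia rates that Section 3.6.1 reports from the earlier outcome trial (11.61% on sacubitril/valsartan and 14% on enalapril) carry no potassium cut-off and cannot stand in for that rate.

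**The case against.** The strongest reply is that the appendix resolves the tension itself. The general sentence says *should*, while the referral to the bands says *will*, and the band is specific and unambiguous. On ordinary reading the specific instruction governs the general one. The body of the protocol points the same way: "The investigator must discontinue study treatment for a given patient if, on balance, he/she believes that continuation would negatively impact the risk/benefit" is mandatory, the same section requires a stop wherever participation might put the patient at risk, and Section 11.1 backs immediate safety action. A site that stops drug at 6.0 breaches nothing mandatory, and most investigators would stop at once.

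It can also be said that the correction may come too late. The SAP amendment is dated 26-Mar-2019, before database lock, and refers to a final review of protocol deviations, so dosing may have been close to finished.

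Most of this stands, and it is why the point is minor. It makes the harmful reading unlikely, but it does not remove the contradiction. A site should not have to rely on a rule of interpretation, or on a clause that excuses deviations, to follow the appendix's own instruction. On timing, the documents give no last-patient date, so whether the change would still reach treated patients cannot be determined.

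**Conclusion.** The concern holds as a low-severity conflict of safety wording. The confirm-first principle is wrong as written for one of the three bands, potassium of 6.0 mEq/L or more, and consistent with the other two. The conclusion rests on the literal text and on the absence of an express exception elsewhere in the protocol. It does not depend on whether 5.3 or 5.5 mEq/L was meant by the predefined values. No delay and no number of affected patients is claimed. The thresholds, the actions within the bands and the immediate stop itself are not in question.

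**What to change.** Add one clause to the end of the general-principle sentence in Appendix 2: *except at potassium of 6.0 mEq/L or more, where study drug is stopped immediately pending confirmation*. The sponsor could name urgent evaluation and treatment in the same clause, since the general sentence literally covers those too. The bands need no change.

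The drafting cost is negligible. Section 11.1 requires approval by the sponsor, by health authorities where required, and by the IRB/IEC before a change takes effect, and Section 4 plans about 80 centers. The clause should therefore go into the next amendment, with a site clarification, and does not justify an amendment of its own. If dosing has ended, it is worth carrying only into related protocols that reuse this appendix.

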### Recommended corrective action for management of hyperkalemia

#### Serum potassium > 5.3 and less than or equal to 5.5 mEq/L

- Confirm potassium concentration in a non-hemolyzed sample
- Reinforce low potassium diet and restriction of food/drinks with high potassium content (e.g. orange juice, melon, bananas, low-salt substitutes etc.)
- Review medical regimen (including dietary supplements and over-the-counter medications) for agents known to cause hyperkalemia. Consider reduction in dose or discontinuation of these agents:
- Aldosterone antagonists (if they are believed to be the most likely cause of hyperkalemia)
- Potassium-sparing diuretics (e.g. amiloride and triamterene) including in combination products with thiazide or loop diuretics
- Potassium supplements, e.g., potassium chloride
- Salt substitutes
- Non-steroidal anti-inflammatory drugs (NSAIDs)
- Cyclo-oxygenase-2 (COX-2) inhibitors
- Trimethoprim and trimethoprim-containing combination products, such as Bactrim® and Septra® (trimethoprim/sulfamethoxazole fixed combination)
- Herbal Supplements:
- For example, Noni juice, alfalfa (*Medicago sativa*), dandelion (*Taraxacum officinale*), horsetail (*Equisetum arvense*), nettle (*Urtica dioica*), milkweed, lily of the valley, Siberian ginseng, hawthorn berries
- Repeat serum potassium measurement within 3 to 5 days
- If serum potassium remains  $> 5.3$  and  $\leq 5.5$  mEq/L, regularly monitor serum potassium levels to ensure stability (suggested once monthly)
- Consider down-titration of study medication, according to investigator medical judgment if he/she believes that adjustment/elimination of concomitant medications is not possible or does not alleviate the side effects of concern medical judgment.

**Serum potassium > 5.5 and < 6.0 mEq/L**

- Confirm potassium concentration in a non-hemolyzed sample
- Consider down-titration or temporarily discontinue study drug according to investigator medical judgment.
- Apply all measures outlined for serum potassium > 5.3 and  $\leq$  5.5 mEq/L
- Repeat serum potassium measurement after 2-3 days
- If serum potassium < 5.5 mEq/L, consider resumption of study drug at lower dose with repeat potassium within 5 days

**Serum potassium greater than or equal to 6.0 mEq/L**

- Immediately discontinue study drug
- Confirm potassium concentration in a non-hemolyzed sample
- Urgently evaluate patient and treat hyperkalemia as clinically indicated
- Apply all measures outlined for serum potassium > 5.3 and < 6.0 mEq/L
- If serum potassium < 5.5 mEq/L, consider resumption of study drug at lower dose with repeat potassium within 5 days

## **15 Appendix 3: Guidelines for the management of blood pressure**

### **Guidelines**

- Investigator should monitor blood pressure closely
- If symptomatic hypotension occurs:
- Correct any treatable cause, e.g. hypovolemia
- If hypotension persists, any antihypertensive drug and non-disease-modifying drugs, such as diuretics, CCBs, nitrates, and  $\alpha$ -blockers, should be down-titrated or stopped first before down-titration of the study drug is considered
- If hypotension persists, the study drug should be down titrated or even temporarily withdrawn. The dose re-challenge and medication adjustment guidelines described in [Section 5.5.5](#) should be adhered to as much as possible.

